#### **9.1.6. Non-serious Adverse Events**

Non serious treatment emergent adverse events will be summarized by SOC, preferred term, study part, dose cohort, and overall. The non-serious TEAE summary is provided to support the clinical trial results summary part of the EU CTR reporting.

#### **9.1.7. Adverse Events of Special Interest (AESI)**

AESIs are defined in the protocol. AESIs will be summarized by SOC, preferred term, study part, dose cohort, and overall.

#### **9.1.8. Adverse Events Leading to Treatment Discontinuation**

An AE leading to treatment discontinuation is an AE where the answer to “Action Taken with FLT201” is “Infusion Stopped” in the Adverse Event eCRF page. Adverse events leading to treatment discontinuation will be presented in a table by SOC, and preferred term, study part, dose cohort, and overall. At each level of participant summarization, a participant is counted once if the participant reported one or more events.

#### **9.1.9. Death**

All participant deaths will be reported in a listing only. Data presented will comprise date of death, days on study, date of last visit, cause of death, autopsy performed (yes, no), and death certificate (yes, no).

### **9.2. Clinical Laboratory Evaluations**

Summary tables presenting observed values and changes from baseline will be presented for clinical laboratory tests with numeric values by study part, dose cohort, and overall, for participants in the Safety Set. Changes from baseline to each scheduled post-baseline visit will be presented.

Laboratory assessments will be performed by a central laboratory. All summaries will be based on the units provided by the laboratory; no conversion will be applied.

All relevant clinical laboratory test results will be classified as Low, Normal, and High, or Normal/Abnormal according to the normal ranges. These categorical data will be summarized in shift tables comparing the results at each scheduled post-baseline visit with those at the baseline visit.

When there are multiple values within a visit for a particular laboratory variable, the worst value will be taken (worst being the smallest value for criteria below a certain threshold or the largest value for criteria above a certain threshold). If a participant has a value below the threshold and above the threshold, the value furthest from the threshold will be chosen.

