12.5.3 Safety

Any clinically significant changes for any safety measure from screening should be reported as an AE.

Physical Examination

The following sites will be examined: head, neck, ears, nose, throat, eyes, chest, lungs, heart, abdomen, skin, and lymph nodes.

The following systems will be assessed: musculoskeletal and neurological.

The participant's height (screening only) and weight will also be measured.

Laboratory Safety Assessments

The following laboratory tests will be performed at a **central** laboratory to assess safety (refer to laboratory manual for details on sample collection and processing):

- Haematology: complete blood count with differential, platelet count. International normalised ratio (INR), partial thromboplastin (PTT).
- Chemistry: sodium, potassium, chloride, phosphate, CO₂, glucose, blood urea nitrogen, serum creatinine, C-reactive protein, hs troponin-T.
- LFTs: albumin, alkaline phosphatase, direct bilirubin, indirect bilirubin, total bilirubin, ALT, and AST.
- The following laboratory tests will be performed at a local laboratory to assess safety:
- LFTs: albumin, alkaline phosphatase, direct bilirubin, indirect bilirubin, total bilirubin, ALT, and AST.

Local LFT laboratory analysis will be utilised to ensure rapid turnaround of results.

Blood samples for tacrolimus levels and CMV testing will be drawn and analysed locally. On days where other clinical assessments are not required these samples may be taken at study site or an alternative location (e.g., participant's home). Management guidelines in the case of CMV reactivation can be found in Appendix 2: Management Guidelines for CMV Reactivation.

If immunosuppressants are implemented at any other time, monitoring for tacrolimus levels and CMV testing (if required) should be undertaken in conjunction with the immunosuppressant dosing and for two weeks following cessation of immunosuppressants (see immunosuppression management plan for further details).

GCase Immune Response

Blood samples will be drawn to assess total anti-GCase antibody titre and neutralising antibody titre. The samples will be analysed at a central laboratory (refer to the laboratory manual for details on sample collection and processing).

AAVS3 Immune Response

Blood samples will be drawn for the assessment of AAVS3 antibody titre and T-cell response, the samples will be analysed at a central laboratory, (refer to the laboratory manual for details on sample collection and processing)

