## 6. Demography and Baseline Characteristics

### 6.1. Demography

Demography data will be summarized by study part, dose cohort, and overall. Individual participant listings will be provided to support the summary table.

Age (year), weight (kg), height (cm) and body mass index (BMI) will be summarized using descriptive statistics (i.e., n, mean, standard deviation, median, minimum, and maximum). Age

category (year), race, sex, ethnicity, and other categorical variables (see list below) will be summarized with frequency tabulations.

Other characteristics include:

- Age group (<65 years, ≥65 years);
- Region (Europe, North America, Latin America);
- Screening hemoglobin level;
- Screening platelet count;
- Screening GCase activity levels (Plasma and DBS);
- Screening GCase concentration;
- Screening chitotriosidase activity (DBS);
- Screening Lyso-Gb1 (Plasma and DBS);
- Screening liver volume (multiples of normal);
- Screening spleen volume (multiples of normal);
- Screening bone mineral density T-score (Lumbar spine and Hips);
- Screening bone mineral density Z -score (Lumbar spine and Hips);
- Screening pulse rate (beats per minute);
- Screening blood pressure (mmHg);
- Screening respiratory rate (breaths per minute);
- Screening body temperature (°C);

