### **9.2.1. Hematology**

All hematology central laboratory tests will be summarized: complete blood count with differential, platelet count, prothrombin time (PT), international normalized ratio (INR), and activated partial thromboplastin time (APTT). All hematology data by participant will be presented in a listing. Note that in the occasions where central laboratory results are missing, local laboratory results will be summarized and listed.

Additionally, plots by-participant for hematology central laboratory tests over time will be produced for the following tests: hemoglobin, platelet count, APTT, and PT.

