## **9.6. Other Safety Data**

### **9.6.1. Liver Function Tests (LFTs)**

LFT data will be collected at each visit and summarized descriptively by laboratory (central, local), study part, dose cohort, and overall. The following laboratory tests will be collected: albumin, alkaline phosphatase, direct bilirubin, indirect bilirubin, total bilirubin, ALT, and AST. LFT data will also be presented in a listing. In addition, ALT, and AST levels and Total bilirubin will be plotted by-participant and laboratory (central, local) over time.

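### SAP 9.2 applies no unit conversion on the premise of one central laboratory, but local haematology (9.2.1) and pooled local liver tests (9.6.1) enter summaries with no rule for a common unit

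*SAP*

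**What the plan says.** SAP 9.2 (Clinical Laboratory Evaluations) starts from the statement that "Laboratory assessments will be performed by a central laboratory". It goes on: "All summaries will be based on the units provided by the laboratory; no conversion will be applied". The same section plans observed values, changes from baseline and shift tables against normal ranges.

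SAP 9.2.1 (Hematology), a subsection of 9.2, covers the complete blood count and the platelet count, and adds: "Note that in the occasions where central laboratory results are missing, local laboratory results will be summarized and listed".

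SAP 9.6.1 handles liver tests apart from 9.2: "LFT data will be collected at each visit and summarized descriptively by laboratory (central, local), study part, dose cohort, and overall". Central and local values are kept separate there, but local values are not split by site or by laboratory. Local liver testing is part of the design. Protocol 12.5.3 explains that "Local LFT laboratory analysis will be utilised to ensure rapid turnaround of results", and Protocol 12.2.1 sets it at two or three times a week.

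The protocol synopsis describes a global multicentre study, and SAP 6.1 lists Europe, North America and Latin America as regions. Neither document names a standard reporting unit for local results or a step that brings them to one.

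**The concern.** With one central laboratory, leaving units alone is harmless because every value of an analyte arrives in the same unit. Once local laboratories contribute, that guarantee goes. Haemoglobin may be reported in g/dL or g/L, platelets per mm³ or ×10⁹/L, and bilirubin in mg/dL or µmol/L. A programmer who follows 9.2 and 9.2.1 literally would average such values as they stand and subtract a central baseline from a local post-baseline value.

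Section 9.6.1 raises the same question for local liver tests. It can also arise within one participant. The protocol allows the infusion week to take place at a different site from follow-up, and liver tests before and after dosing on Day 1 are local. One participant's local series may therefore come from more than one laboratory.

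The study is wholly descriptive (SAP 4.2), so the summary tables are the results. Part 1 cohorts are planned with at least two participants and possibly a third, so one value in the wrong unit dominates its row.

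**Working it through.** The plan gives no figure to reproduce. The check has two parts: which unit rule applies to each kind of result, and how far one unconverted value would move a summary.

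**Which rule applies**

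| Result | SAP section | Source | Unit rule |
|---|---|---|---|
| Central haematology and chemistry | 9.2, 9.2.1, 9.2.2 | one laboratory | no conversion; consistent |
| Local haematology replacing a missing central result | 9.2.1 | site laboratory | inherits no conversion from 9.2 |
| Central liver tests | 9.6.1 | one laboratory | none stated; consistent |
| Local liver tests | 9.6.1 | many site laboratories in one local category | none stated |

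Rows 2 and 4 are the problem. In row 2 the rule applies but its premise has failed. In row 4 no rule exists.

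**Size of one unconverted value**

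Assumptions, not taken from the documents: all *n* participants share the same true value *v*, and one is reported in a unit that multiplies the number by *k*. Then

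mean = *v* × (*n* − 1 + *k*) / *n*

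and, with true change 0 and a correct baseline,

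mean change = *v* × (*k* − 1) / *n*.

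*Haemoglobin*, *v* = 13 g/dL, *k* = 10 (g/L):
- *n* = 3: mean = (13 + 13 + 130) / 3 = 52.
- That participant's change = 130 − 13 = +117; cohort mean change = 117 / 3 = +39.
- *n* = 2: mean = (13 + 130) / 2 = 71.5; mean change = 117 / 2 = +58.5.
- *n* = 12 (planned Part 1 total): mean = (11 × 13 + 130) / 12 = 22.75; mean change = 117 / 12 = +9.75.

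*Platelets*, *v* = 120,000/mm³, *k* = 0.001 (×10⁹/L):
- *n* = 3: mean = (120,000 + 120,000 + 120) / 3 = 80,040; mean change = (120 − 120,000) / 3 = −39,960.

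*Local total bilirubin*, *v* = 0.6 mg/dL, *k* = 17.1 (µmol/L):
- The one value becomes 0.6 × 17.1 = 10.26.
- *n* = 3: mean = (0.6 + 0.6 + 10.26) / 3 = 3.82.

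The haemoglobin error would be obvious on sight. The platelet mean would not, because 80,040/mm³ is a credible value in this disease and could be read as a real fall.

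After conversion to one unit, *k* = 1 in both formulas. The means return to 13, 120,000 and 0.6, and the mean change to 0, at any *n*.

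**The case against.** The strongest reply is that the no-conversion sentence directly follows the central-laboratory statement, so the laboratory it refers to is most naturally the central one. On that reading the SAP does not forbid converting local results; it is silent about them. This is fair, and it is decisive for 9.6.1, which lies outside 9.2. It helps less for 9.2.1, which sits under the rule and brings local values into the summaries. Even on the generous reading, those values have no unit rule.

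Three stronger readings are tempting, and the documents do not support them.

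- *The hepatic safety conclusions are compromised.* Central liver tests are taken at every scheduled follow-up visit and summarised separately, so a single-laboratory summary exists whatever the local units are. A dose-limiting toxicity is a participant-level judgement (Protocol 13.2). The ALT events of special interest are judged against normal or the participant's own baseline, and the serial-rise criterion requires the same laboratory (Protocol 14.2.9). None of these uses a pooled local mean.
- *The secondary efficacy results for haemoglobin and platelets are contaminated.* Protocol 12.5.2 assigns both to the central laboratory, and the substitution sentence is in the safety section. SAP 8.3 does not say whether substituted values enter its tables. The question is open, not answered.
- *Mixing will be common.* No local haematology is scheduled. The local tests are pregnancy, liver function, CMV and tacrolimus, with SARS-CoV-2 before dosing. A substitution needs both a missing central result and an unscheduled local one.

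It is also true that minimum, maximum and full listings are planned (SAP 4), so a gross error would often be seen. The data management plan (Protocol 16.1.4) covers quality checks and may standardise units, but the documents do not say that it does. These safeguards lower the chance of an error going unnoticed. They do not change what the SAP tells the programmer to do.

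**Conclusion.** The point stands as a drafting defect that should be corrected. A stated rule, followed literally, can give a wrong result in the 9.2.1 haematology summaries, and the local liver summaries in 9.6.1 have no unit rule. For local liver tests the gap concerns routine, frequent data; for haematology it is likely to be rare.

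The size depends on assumptions about local units, which the documents do not give. If one of three participants is in another unit, the cohort mean is wrong by a factor of 4 for haemoglobin (52 against 13) and about 6.4 for bilirubin (3.82 against 0.6), and falls by a third for platelets. The cohort mean change in haemoglobin is +39; the +117 belongs to one participant and should not be read as a cohort figure. If all local laboratories already use the central laboratory's units, there is no numerical effect.

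**What to change.** In the SAP:

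1. Limit the no-conversion sentence in 9.2 to central laboratory results.
2. In 9.2.1, convert any substituted local haematology result to the central laboratory's unit before it enters a summary, shift table, plot or change from baseline. Flag it in the listing.
3. In 9.6.1, express local liver results in one common unit per analyte before any summary or plot.
4. Classify local values as low, normal or high against the range of the laboratory that produced them.
5. In 8.3, state whether substituted local values enter the secondary haemoglobin and platelet tables.

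Optional: summarise local ALT, AST and bilirubin also as multiples of each laboratory's upper limit of normal, which would deal with differing ranges as well as units, and repeat the haemoglobin and platelet changes without substituted values.

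The cost is a few sentences of SAP text and routine conversion programming. It requires the unit and normal range to be available with each local result. No protocol amendment or extra participant data is needed.

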### **9.2.1. Hematology**

All hematology central laboratory tests will be summarized: complete blood count with differential, platelet count, prothrombin time (PT), international normalized ratio (INR), and activated partial thromboplastin time (APTT). All hematology data by participant will be presented in a listing. Note that in the occasions where central laboratory results are missing, local laboratory results will be summarized and listed.

Additionally, plots by-participant for hematology central laboratory tests over time will be produced for the following tests: hemoglobin, platelet count, APTT, and PT.

### **9.2.2. Serum Chemistry**

The following laboratory tests will be summarized: sodium, potassium, chloride, phosphate, bicarbonate, glucose, blood urea nitrogen, serum creatinine, C-reactive protein, hs troponin-T. All chemistry data by participant will be presented in a listing.

### **9.2.3. Pregnancy Testing**

A listing of pregnancy test results will be presented combining serum and urine tests.

## **9.3. Vital Signs**

Summary tables presenting observed values and changes from baseline will be presented for vital sign data, including systolic blood pressure (mmHg), diastolic blood pressure (mmHg), body temperature (°C), pulse rate (beats per minute), and respiration (breaths per minute) by study part, dose cohort, and overall. Changes from baseline to each scheduled post-baseline visit will be presented. All vital sign data will be presented in a listing.

## **9.4. Physical Examinations**

A table will summarize physical examination results by study part, dose cohort, and overall. Each visit captures the status of a body system and any finding associated with the body system as normal, abnormal, or not done. The summary will include the number and percentage of participants with each physical examination outcome for the following body systems: skin; head, neck, eyes, ears, nose, and throat (HEENT); respiratory; cardiovascular; gastrointestinal; endocrine/metabolic; genitourinary; neurological; blood/lymphatic; musculoskeletal; and other. Physical examination results for all participants will be presented in a listing.

## **9.5. Electrocardiogram**

Summary tables will be presented for 12-lead ECG data including ventricular rate (bpm), PR interval (msec), QRS duration (msec), QT interval (msec), and QTcF interval (msec), QTcB interval (msec), QTcLC interval (msec), QTcV interval (msec), by study part, dose cohort, and overall. Observed results at each visit will be presented.

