15.3 Analysis of Primary Safety Endpoints

Dose-limiting Toxicities

All DLTs will be summarised by cohort/dose level.

Although the dose escalation is based on an algorithm, the final data may be used, for example, to model the DLTs as a function of dose, adjusted for any potential confounders, to further refine any estimate of the MTD (e.g., to determine the probability of toxicity closest to a given threshold toxicity at some observed dose level). The uncertainty around the estimate of the true DLT rate may be provided in terms of 95% confidence intervals or 95% credible intervals.

Adverse Events

Frequency of treatment-emergent AEs and SAEs will be calculated for each body system and preferred term, and by dose level, for number of events and number of participants reporting the event. The severity of the AEs and the relationship to study medication will be summarised for each body system and preferred term by cohort/dose level.

Other Safety Endpoints

Safety endpoints including the following will be summarized descriptively by cohort/dose level.

- Change from baseline in laboratory data
- Change from baseline in 12-lead ECG data
- Change from baseline in physical examination data
- Change from baseline in vital signs data.

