**Table 2-1 Primary Objective and Endpoints - Safety**

Primary Objective	Primary Endpoints
To assess the safety and tolerability of a single IV administration of FLT201 in adults with Gaucher disease type 1 (previously treated and previously untreated).	
Primary safety variable: incidence of TEAEs (including DLTs) from Day 1 to the last follow-up visit.
 
Other safety endpoints: incidence of AEs, SAEs, and changes from baseline in vital signs, 12-lead ECG, physical examination, and laboratory assessments from Day 1 to the last follow-up visit.

Abbreviations: AE=adverse event; DLT=dose-limiting toxicity; ECG=electrocardiogram; IV=intravenous; SAE=serious adverse event; TEAE=treatment emergent adverse event.
	

Table 2-2 presents the secondary objectives and endpoints.

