## **4. General Statistical Considerations**

All study data collected will be presented in data listings, and all relevant data will be tabulated and summarized by study part, dose cohort, and overall, unless stated otherwise.

Continuous data will be described using descriptive statistics (i.e., n, mean, standard deviation, median, minimum, and maximum). Categorical data will be described using the count and percentage in each category. For the summary statistics of all numerical variables unless otherwise specified, minimum and maximum will be displayed to the same level of precision as reported. Mean and median will be displayed to one level of precision greater than the data collected. Standard deviation, standard error, and confidence intervals will be displayed to two levels of precision greater than the data collected.

Missing data will not be imputed. All analyses will be based on observed cases for the safety population unless specified otherwise.

Clinical laboratory and PK results that are below the lower limit of quantification (BLQ/LOQ), below the limit of detection (LOD), above the upper limit of quantification (ULOQ) or missing will be displayed as such in the data listings.

To calculate descriptive statistics and PK parameters, all BLQ, LOQ and LOD results will be treated as half of the BLQ/LOQ/LOD values whereas all ULOQ values will be treated as the ULOQ values as applicable.

The end of the study will be defined as the last visit by the last participant. All participants will be followed up for at least 5 years in a separate long-term follow-up study.

Unless specified otherwise, baseline will be defined as the last non-missing measurement prior to the infusion of IMP.

Change from baseline is defined as: post-baseline value – baseline value.

Study Day 1 is the calendar day of the IMP infusion. Subsequent study days are calculated as the date of assessment/event – date of infusion + 1. Pre-infusion study days are calculated as date of assessment/event – date of infusion. There is no Study Day 0.

All data are summarized based on the visit name collected on the eCRF page.

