#### **9. Safety Analysis**

The safety profile is based on the incidence of Treatment Emergent Adverse Events (TEAEs) including DLTs and Serious Adverse Events (SAEs), as well as the change from baseline in standard clinical laboratory assessments, physical examination findings, vital signs, and 12-lead ECG recordings and will be summarized descriptively.

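### SAP 9.5 specifies only observed ECG values, in conflict with the change-from-baseline ECG endpoint stated in SAP Table 2-1, the SAP 9 lead-in and protocol 15.3

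*SAP*

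**What the plan says.** The endpoint is stated consistently. SAP Table 2-1 lists, among the other safety endpoints under the primary objective, "changes from baseline in vital signs, 12-lead ECG, physical examination, and laboratory assessments from Day 1 to the last follow-up visit". Protocol 15.3 includes "Change from baseline in 12-lead ECG data" among the safety endpoints to be summarised descriptively by cohort or dose level. The lead-in to SAP 9 repeats it: the safety profile rests on adverse events "as well as the change from baseline in standard clinical laboratory assessments, physical examination findings, vital signs, and 12-lead ECG recordings", and these are to be summarised descriptively.

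SAP 9.5, the section that specifies the ECG output, names the heart rate, the intervals and four QT corrections, gives the grouping by study part, dose cohort and overall, and ends with "Observed results at each visit will be presented". It mentions neither change from baseline nor a listing.

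The neighbouring sections are fuller. SAP 9.3 on vital signs names observed values and changes, and states "Changes from baseline to each scheduled post-baseline visit will be presented". SAP 9.2 does the same for laboratory tests and adds shift tables.

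Two general rules in SAP 4 also apply. "All study data collected will be presented in data listings", and continuous data are described with "descriptive statistics (i.e., n, mean, standard deviation, median, minimum, and maximum". SAP 4 also defines baseline and change from baseline for general use.

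**The concern.** The section a programmer would follow for the ECG tables asks for less than the endpoint it serves. If 9.5 is taken literally, change from baseline in ECG is not tabulated, although both documents name it as a safety endpoint. Section 15 of the protocol requires departures from the protocol's planned analyses to be set out in the SAP. SAP 14 lists four changes, and this is not one of them. Either 9.5 is incomplete or SAP 14 is.

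ECG is not an incidental measurement here. Protocol 6.5.3.1 reports mild, transient myocarditis in a study of another product with the same capsid, and protocol 14.2.9 makes both myocarditis and clinically significant ECG change adverse events of special interest. ECGs are read locally at the sites (protocol 12.5.3), so a numerical within-participant summary would complement the investigators' judgement.

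**Working it through.** No figure in the plan depends on this point, because the sample size is based on feasibility and nothing is tested. The check has two parts: a comparison of the texts, and simple arithmetic on what each kind of table can show.

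**Texts side by side**

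| Place | ECG output called for |
|---|---|
| Protocol 15.3 | Change from baseline, by cohort/dose level |
| SAP Table 2-1 | Change from baseline, Day 1 to last follow-up |
| SAP 9 lead-in | Change from baseline, descriptive |
| SAP 9.5 | Observed results at each visit |
| SAP 14 | No departure declared for ECG |

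Three places ask for change, one specifies observed values only, and the list of departures is silent.

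**What observed summaries can and cannot show**

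The ECG values below are assumptions, since neither document gives a QT threshold or expected value. The cohort size of three is the planned minimum of two plus the optional third participant (protocol 8.1).

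1. *Offsetting shifts.* Baseline 380, 410, 440 ms; post-baseline 440, 410, 380 ms.
   - Observed at both times: mean (380 + 410 + 440)/3 = 410, median 410, minimum 380, maximum 440. All four are unchanged.
   - Changes: +60, 0, -60. Mean 0, minimum -60, maximum +60.
2. *One participant shifts.* Baseline 380, 410, 440 ms; post-baseline 440, 410, 440 ms.
   - Observed: mean 410 to 430, median 410 to 440, minimum 380 to 410, maximum 440 to 440.
   - Changes: +60, 0, 0. Mean 20, median 0, minimum 0, maximum +60.
   - The observed table shows that something moved, but its maximum is unchanged and the 60 ms shift cannot be read from it.
3. *What mean change adds.* With complete pairs, mean change = mean post-baseline - mean baseline. In case 1 this is 410 - 410 = 0, and in case 2 it is 430 - 410 = 20. Mean change therefore repeats what the observed means already show. The added information is in the minimum and maximum of change.
4. *Dilution.* A shift of d ms in one of n participants moves the mean by d/n. For d = 60 that is 30 ms at n = 2, 20 at n = 3, 10 at n = 6, 5 at n = 12 and 3.3 at n = 18. Dilution is modest within a cohort of two or three and marked in the overall column.

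**The case against.** The strongest reply is that the SAP does commit to the analysis. The sentence that opens SAP 9 ends "vital signs, and 12-lead ECG recordings and will be summarized descriptively", and it governs 9.5. With baseline and change defined in SAP 4, a programmer who reads the whole section would produce the change columns. This stands in part. A reader might infer from 9.5 that the SAP has dropped the endpoint, and the documents do not support that. They show two parts of one section in conflict, most likely through an omission in 9.5. The lead-in does not cure the conflict, because 9.5 is the detailed specification and says something narrower.

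A reader might also infer that individual QT shifts would be lost in cohort means. The documents do not support that either. All collected data are listed, so in cohorts of one to three each participant's change can be worked out from the listing. Summaries report more than the mean. ECG changes judged clinically significant are adverse events of special interest, tabulated under SAP 9.1.7, and high-sensitivity troponin-T is summarised as a laboratory test under SAP 9.2. What remains is narrower: the observed minimum and maximum can miss paired shifts, as case 1 shows, and a listing of raw values is not a summary of the endpoint.

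It may also be tempting to ask for counts above fixed QTc increases, or for one QT correction to be named as primary. Neither document sets such a threshold, prefers a correction, or links FLT201 to QT prolongation. Those requests would be preferences and form no part of this point.

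Finally, the named dose-escalation rules (protocol 13.3.1.1 to 13.3.1.3) use dose-limiting toxicity, GCase activity and a dose ceiling. No named rule depends on the ECG table.

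**Conclusion.** The point holds as an internal inconsistency. SAP 9.5 specifies observed ECG values only, while SAP Table 2-1, the SAP 9 lead-in and protocol 15.3 call for change from baseline, and SAP 14 declares no departure. It is a minor correction to a descriptive safety output, with no effect on the sample size, any test or any named escalation rule. The numerical cases are assumed and show only that observed summaries can miss paired shifts; they say nothing about how likely such shifts are. The conclusion rests on the wording of the two documents. ECG table shells are not among them, so whether the programmed table would follow 9.5 or the lead-in cannot be determined.

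**What to change.** Amend SAP 9.5 to present observed values and change from baseline at each scheduled post-baseline visit, by study part, dose cohort and overall, using the standard statistics in SAP 4 so that the minimum and maximum of change appear. It would be tidy to name the ECG listing in 9.5 as well, although the general rule already covers it. If leaving out change from baseline was deliberate, declare it in SAP 14 and reconcile Table 2-1 and the SAP 9 lead-in with it.

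The cost is one edited sentence and extra columns in a planned table. No new data are needed: a pre-infusion ECG is scheduled at Day -1 (protocol 12.1.3), and baseline and change are already defined.
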